# LABORATORY EVALUATIONS

Blood samples will be obtained to examine vaccine safety and immunogenicity.

# Sample collection, distribution and storage

Samples to evaluate vaccine immunogenicity will be obtained and processed at the field study site and transported to icddr,b's Immunology Laboratory. Research specimens collected for the immunogenicity time points will be separated into aliquots by the icddr,b Immunology Laboratory per study specific procedures and processed or stored for immunological analysis and, where necessary, for potential shipment to UG and/or SBioPharma. Samples will be stored properly in controlled-temperature refrigerators/freezers. Backup generators are available for proper sample storage.

Stool samples will be obtained and processed at the field site and transported daily to the icddr,b Immunology Laboratory. Samples will be processed and tested according to icddr,b laboratory standard operating procedures (SOPs) for fecal specimens. Thereafter, residual specimens will be stored at -20° C.

# Safety clinical laboratory assays

During screening and at Day 7, blood samples will be collected for safety clinical laboratory evaluations. Samples will be packaged and transported to the clinical laboratory according to SOPs and tested. Standard clinical laboratory tests for the purpose of inclusion and exclusion of potential participants and for safety monitoring will be carried out by the icddr,b Clinical Laboratory Services.

# Immunological assays

All research samples will be collected at the urban field site in Mirpur, Dhaka. Samples will be packaged and transported via official transport to the Immunology Laboratory. Immunologic assays will be performed as per written SOPs and will be a part of the study documentation. Stools will be processed for total antigen specific fecal IgA in the Immunology Laboratory (stool cultures will be done when indicated in the Microbiology Laboratory). The assays will occur as outlined in the Study Event Schedule. Samples will be stored so that all specimen time points can be tested together for each participant.

The following prioritization scheme will be applied to the vaccine antigens according to analysis as specimen volumes allow:

- ALS IgA: LTB > CFA/I > CS3 > CS6 > CS5 > O78LPS
- Fecal SIgA/total SIgA: LTB > CFA/I > CS3 > CS6 > CS5 > O78LPS
- PlasmaIgA; LTB > 078 LPS > CFA/I > CS3 > CS6 > CS5
- PlasmaIgG: LTB > 078 LPS
- T cell and other immune responses: LTB > CFA/I > CS3 > CS6 > CS5

#### Sample Size Calculation and Outcome (Primary and Secondary) Variable(s)

Clearly mention your assumptions. List the power and precision desired. Describe the optimal conditions to attain the sample size. Justify the sample size that is deemed sufficient to achieve the specific aims.

#### Sample Size Calculation:

Safety will be assessed by analyses of the following primary endpoints (events), where the unit of analysis in each case will be the proportion of participants with at least one event:

- Solicited gastrointestinal reactions
- Solicited systemic reactions
- Unsolicited Adverse events
- Adverse events where there is a reasonable possibility that the study product caused the event, i.e., are suspected adverse reactions
- Serious adverse events

The sample size for this study was selected to detect frequent adverse events. Given a planned sample size of groups of 15 adults, toddlers, and younger children each receiving one of varying dose levels of ETVAX with and without dmLT, the study will have an approximately 80% and 90% chance of observing at least one serious adverse event or adverse event of special interest for events that occur at a rate of 10.3% and 14.3%, respectively. Additionally, if no serious adverse events are observed in 15 participants, the upper bound of the one-sided 95% confidence interval on the rate of serious adverse event occurrence is approximately 18%.

For infant cohorts with 30 participants per dose group, the study will have an approximately 80% and 90% chance of observing at least one serious adverse event or adverse event of special interest for events that occur at a rate of 5.3% and 7.4%, respectively. If no serious adverse events are observed in 30 participants, the upper bound of the one-sided 95% confidence interval on the rate of serious adverse event occurrence is approximately 9.5%.

For infant cohorts, with 30 participants per group, this study is designed to provide approximately 73% power to detect as low as a 2-fold difference in geometric mean fold rise (post-vaccination / baseline) between comparisons of two groups

with varying doses of ETVAX and dmLT levels. This power calculation was based on the variability estimate, log10 standard deviation of 0.6, for CS6 obtained from a previous study of the vaccine in Sweden (VAC 003/OEV-121) and two-sample t-test using the 5% two-sided Type I error rate and 10% drop-out rate.

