	(0%, 0-13)	(60%, 41-77)	(54%, 33-74)	(67%, 45-84)

**Table 3.** Frequencies of IgA respondersa against the different primary vaccine antigens in ALS and fecal specimens (per protocol analysis sets).

a Cumulative response rates after one or two immunizations. Fold rises  $\geq 2$  were considered as responses in all assays.

b Percentage of responders, 95% CI

c If only subjects with a day 0 specimen were included in the analysis, 10/16 subjects (63%) responded to CS3 in fecal specimens. For all other antigens and groups, comparable frequencies were recorded if all subjects or only subjects with a day 0 specimen were included.

\*\*\* P<0.001 for comparisons of all vaccine groups (B, C and D, respectively) with the placebo group (A) for all primary antigens (one-tailed Fisher's exact test, with Holm's correction). (42)

Frequency of subjects a	(A)	(B)	(C)	(D)
responding to:	Placebo	Vaccine	Vaccine	Vaccine
1 8			+ 10 µg dmLT	+ 25 μg dmLT
	(n=20)	(n=23)	(n=23)	(n=20)
5 antigens b	0%	74%	83%	75%
4 antigens	0%	17%	4%	10%
3 antigens	5%	0%	4%	0%
2 antigens	10%	4%	4%	10%
1 antigen	5%	0%	4%	0%
0 antigen	80%	4%	0%	5%

**Table 4.** Frequencies of IgA responders against different numbers of primary vaccine antigens in ALS and/or fecal specimens

a Only subjects from whom both fecal and ALS specimens were available

bLTB, CFA/I, CS3, CS5, CS6

Based on these highly encouraging results, OEV-122 is proposed to study the safety and immunogenicity of the vaccine when given to children living in areas endemic for ETEC.

### Live Attenuated ACE527 Vaccine with and without dmLT - VAC 006

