The icddr,b Dhaka hospital treats more diarrheal patients from Mirpur than from any other part of Dhaka. It was observed that most of the isolated cases from the diarrheal patients are *V. cholerae* or ETEC and their general living and hygienic condition is poor with scarcity of safe drinking water and sharing kitchen and toilet. In a birth cohort study in this community, icddr,b has evaluated the natural history of ETEC infections and found that ETEC was the most common pathogen and was isolated in around 20% cases with an incidence of 0.5 episodes/child/year in 0-2 years old children [16]. From the large feasibility study of cholera vaccine where they also conducted passive surveillance for enteric pathogens, it was observed that ETEC incidence rate varies from 1.1 to 1.47 /1000 /year and incidence rate is comparatively high in children less than 5 years old (4.5/1000/year)(Protocol# 12090). The 2% systemic surveillance data from icddr,b suggests that among the diarrheal specimens, ETEC isolation rate is 14% (1996-1998) and 11% (2007-2012) in all age groups. Recently it was observed that of the distribution, 52% ETEC was isolated from those over five years of age and 48% in younger age groups, in which 14 to 20% are severely dehydrated.

This Phase I/II trial will serve to assess whether ETVAX is safe and provides mucosal as well as systemic immune responses against the key protective antigens when tested in different age-groups in Bangladesh. This study provides an opportunity to test the safety profile of a mucosal adjuvant in adults and children, as well as provide the opportunity to potentially assess the ability of dmLT to further enhance the mucosal and systemic antibody responses to key antigens in the ETVAX vaccine among age groups in developing country sites, like Bangladesh, that have proved refractory to oral immunization with enteric vaccines. In addition, this study also allows for the evaluation of the potential dose-sparing effect of dmLT when combined with a lower dose of vaccine. Finally, protective efficacy results observed in the VAC 006 trial substantiate the rationale for dmLT inclusion in this vaccine candidate. This clinical trial is considered an essential study along the critical path of the overall clinical development plan before determining whether the vaccine can be tested for protective efficacy in children in developing countries.

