# **Continued Eligibility Criteria**

Fulfilment of all of the following continuing eligibility criteria is required for all participants to receive their second vaccination (Day 14). If a participant does not meet the following continuing eligibility criteria prior to receiving their second immunization, vaccination can be deferred by up to two days. However, if a participant falls outside this deferred window, he/she will not receive the second vaccination but encouraged to continue all safety follow-up activities per protocol.

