#### Per Protocol Populations

The per protocol populations will be specified per sample and antigen type. All participants in the FA population who receive both doses of the same study vaccine and have post second dose (all sample types) and pre-vaccination (stool and plasma) immunogenicity measurement(s), with no major protocol or laboratory test SOP violations that are determined to potentially interfere with the immunogenicity assessment of the study vaccine, will be included in the per protocol populations. These populations will serve as the primary analysis populations for the immunogenicity objectives.

The specific criteria for exclusion of subjects from the Per Protocol Populations will be established before breaking the blind and will be based on the blinded review of protocol and laboratory test SOP violations

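### The 10% loss in the infant GMFR power is about half the 17–20% loss of evaluable CS6 samples in the trial that supplied the SD; about 24–25 infants per group are more likely than 27

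*Protocol*

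**What the plan says.** The power statement is in the Sample Size Calculation of the protocol. "For infant cohorts, with 30 participants per group", it claims "approximately 73% power to detect as low as a 2-fold difference in geometric mean fold rise" between two groups that differ in ETVAX dose or dmLT level. The inputs are a log10 SD of 0.6 for CS6, taken from OEV-121, and a "two-sample t-test using the 5% two-sided Type I error rate and 10% drop-out rate". The assay behind the SD is not named.

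Under Per Protocol Populations, the sets that are primary for immunogenicity are narrower than the set of participants who stay in the trial: "The per protocol populations will be specified per sample and antigen type". A participant needs both doses, a post-dose-2 result, a pre-vaccination result for stool and plasma, and no major violation that could interfere with the immunogenicity assessment.

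The background section on OEV-121 reports results from the trial that supplied the SD. Table 3 gives IgA responder frequencies "against the different primary vaccine antigens in ALS and fecal specimens (per protocol analysis sets"), with denominators by arm. Table 2 gives the number dosed by arm.

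**The concern.** The calculation borrows the SD from OEV-121 but not that trial's evaluable fraction, although the protocol prints both. Participant drop-out is also a different quantity from what limits a per-protocol set defined by sample and antigen. A participant can complete follow-up and still have no usable CS6 result.

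The infant comparisons of dose and dmLT level inform later development, so their stated power should describe the population that will be analyzed. If only the arithmetic of the power figure were corrected and the 10% kept, the new figure would probably still be somewhat too favorable.

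**Working it through.** **1. The plan's own figure.** Inputs from the Sample Size Calculation: 30 per group, 10% loss (27 per group), δ = log10(2) = 0.301, SD 0.6, two-sided 5%. The power is that of a two-sample t-test with noncentrality δ / (SD·√(2/n)) and 2n − 2 degrees of freedom.

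- n = 27: 0.301 / (0.6·√(2/27)) = 1.84 on 52 df; power 44.0%. The normal approximation gives 45.4%.
- n = 30, no loss: about 48%.
- About 73% appears at n = 54 per group, which would be 60 less 10%. The protocol contains no such group size.

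The printed 73% is therefore not reproduced from its stated inputs. That is a larger and separate fault in the same sentence. The loss assumption is assessed below on the stated group size of 30.

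**2. Evaluable CS6 samples in OEV-121** (numbers at dose 1 from Table 2, CS6 denominators from Table 3):

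| Arm | Dose 1 | ALS | Fecal |
|---|---|---|---|
| Placebo | 34 | 24 | 26 |
| Vaccine | 35 | 27 | 30 |
| Vaccine + 10 µg dmLT | 30 | 28 | 24 |
| Vaccine + 25 µg dmLT | 30 | 24 | 24 |
| All arms | 129 | 103 | 104 |
| Vaccine arms | 95 | 79 | 78 |

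Loss over all arms: ALS 26/129 = 20.2%, fecal 25/129 = 19.4%. Loss in the vaccine arms: ALS 16/95 = 16.8%, fecal 17/95 = 17.9%. The planned 10% is 0.50 to 0.59 of these values.

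Dose 2 was taken by 34 + 34 + 30 + 28 = 126 of 129, so only 3 (2.3%) missed it. Most of the loss was therefore missing or unusable samples, or per-protocol exclusion.

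**3. Carried to 30 infants per group.** Vaccine arms: 30·79/95 = 24.9 and 30·78/95 = 24.6. All arms: 30·103/129 = 24.0 and 30·104/129 = 24.2. That is about 24–25 evaluable against the planned 27.

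**4. Effect on power** (same formula):

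| Evaluable per group | Basis | Noncentrality | Power |
|---|---|---|---|
| 27 | planned 10% loss | 1.84 | 44.0% |
| 25 | vaccine arms, 17–18% | 1.77 | 41.2% |
| 24 | all arms, 19–20% | 1.74 | 39.8% |

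The difference is 2.8 to 4.2 points. These are unadjusted 5% tests. The Immunogenicity Analysis section applies Holm's correction across infant treatment groups, which would lower power further.

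**5. Missed second doses in infants.** Under Continued Eligibility Criteria, diarrhea in the previous 7 days bars the second dose unless a deferral of up to two days resolves it: "However, if a participant falls outside this deferred window, he/she will not receive the second vaccination". The Scientific Rationale says that "ETEC was the most common pathogen and was isolated in around 20% cases with an incidence of 0.5 episodes/child/year in 0-2 years old children". If the 20% is read as ETEC's share of diarrhea episodes, the total is 0.5/0.20 = 2.5 episodes per child-year. The share barred is then about 2.5·7/365 = 4.8%, or 2.5·5/365 = 3.4% if deferral rescues the earliest episodes. By itself this fits inside 10%, but it uses up part of the allowance before any sample is lost.

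**The case against.** The strongest objection is that the comparison carries losses in Swedish adults over to infants in Dhaka, for whom the protocol gives no sample-loss rate. That stands, and it limits the conclusion to what is likely. The documents contain reasons on both sides.

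- Toward more loss: infants give 3.5 mL of blood per visit against 10 mL in adults. Antigens are run as volume allows, with CS6 fourth in the ALS and fecal order. The Table 3 fecal counts include adults without a day 0 specimen (footnote c: for CS3 in the 10 µg arm, 16 of the 24 had one), whereas this protocol requires a baseline stool result.
- Toward less loss: a backup stool is taken on Day 0, stool is collected twice after dose 2, the ALS per-protocol set needs no baseline sample, and an alternate may be dosed if a participant vomits after dose 1.

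The loss also depends on the assay and antigen. ALS for LTB in OEV-121 had 29 + 29 + 29 + 26 = 113 of 129 evaluable, a 12% loss that is close to the planned 10%. Plasma counts are not shown. A reader might infer that the CS6 loss applies to every immunogenicity endpoint; Table 3 does not support that.

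A reader might also add the diarrhea exclusion to the adult loss and arrive at 25%, or 22 per group. The documents do not yield that figure, and the adult losses already contain some missed second doses.

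Finally, the sample size was chosen to detect frequent adverse events, the protocol calls the immunogenicity comparisons exploratory, and the development plan allows an expanded phase II study if this trial does not settle dose and adjuvant. All of this lowers the stakes, but it does not make the stated input match the protocol's own data.

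**Conclusion.** The point holds as a correction of a planning input. The "10% drop-out rate" is about half the 17–20% loss of evaluable CS6 ALS and fecal samples in the trial that supplied the SD. The best-matched figure is the 17–18% loss in the vaccine arms, because the powered comparison is vaccine against vaccine. It gives about 25 per group and 41% power; the all-arms loss gives 24 and 40%. Against 44% at 27, the cost is about 3–4 points.

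This rests on two assumptions: infant CS6 loss resembles that of adults in OEV-121, and the SD of 0.6 belongs to an ALS or fecal measure. Neither is stated in the protocol.

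Two stronger readings are not supported. One is that the infant analysis is certain to have fewer than 27 per group; the documents make this likely and no more. The other is that the loss assumption explains the gap between 44% and 73%; it does not, since 73% fails at the planned 10% loss as well. Correcting the loss rate is useful only if the 73% is replaced at the same time.

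**What to change.** In the Sample Size Calculation, name the assay to which the SD of 0.6 belongs. Replace the drop-out rate with an evaluable-sample rate for that assay, citing Table 3 where it applies (for CS6, about 80–83% evaluable in ALS and fecal samples). State that this rate comes from adults.

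Restate the power from 30 enrolled per infant group over 10–20% loss: about 44% at 27 evaluable, 41% at 25 and 40% at 24, for SD 0.6, a 2-fold difference and a two-sided 5% test before Holm's correction. These figures replace the 73%.

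The cost is a change of wording and a less favorable stated power. No participants, visits or samples are added.

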# **Outcome variables:**

Primary Safety Endpoints

- Number of SAEs
- Number of AEs
- Number of vaccine induced reactogenicity events

Secondary Immunology Endpoints

- Antibody response (≥two-fold increase in antibody titers between baseline and post-immunization), Geometric Mean Titer (GMT), and Geometric Mean Fold Rise (GMFR) between baseline and post-immunization to CFA/I, CS3, CS5, CS6 and LTB as measured by ALS IgA
- Antibody response (≥two-fold increase in antibody titers between baseline and post-immunization), GMT, and GMFR to CFA/I, CS3, CS5, CS6 and LTB as measured by fecal SIgA.
- Antibody response (≥two-fold increase in antibody titers between baseline and post-immunization), GMT, and GMFR to CFA/I, CS3, CS5, CS6 and LTB as measured by plasma IgA.
- Antibody response (≥two-fold increase in antibody titers between baseline and post-immunization), GMT, and GMFR to CFA/I, CS3, CS5, CS6 and LTB as measured by plasma IgG.
- Antibody response (≥two-fold increase in antibody titers between baseline and post-immunization), GMT, and GMFR to O78 as measured by ALS IgA, fecal SIgA, and/or plasma IgA.

Exploratory Immunology Endpoints

- T cell immune responses
- Neutralizing antibody geometric mean titers (GMT) and
- Avidity of immune responses
- Immunoproteomic profile of vaccine induced antibody responses in plasma or intestinally derived samples

# Data Analysis

Describe plans for data analysis, including stratification by sex, gender and diversity. Indicate whether data will be analysed by the investigators themselves or by other professionals. Specify what statistical software packages will be used and if the study is blinded, when the code will be opened. For clinical trials, indicate if interim data analysis will be required to determine further course of the study.

# Overview and general design

This study is a randomized, double-blind, dose-escalation, descending age clinical trial to assess the safety and immunogenicity of the inactivated whole cell ETVAX vaccine administered alone and with dmLT adjuvant as compared to a placebo (bicarbonate buffer). The primary objectives are to evaluate the safety and tolerability of the inactivated whole cell ETVAX vaccine with and without dmLT adjuvant in adults, toddlers, young children and infants.

The secondary objectives are:

- 1. To assess vaccine induced IgA antibody responses in lymphocyte secretions (ALS) against LTBD, CFA/I, CS3, CS6 and CS5 in descending age-groups in Bangladesh
- 2. To evaluate vaccine induced fecal secretory IgA (SIgA) antibody responses against CFA/I, CS3, CS5, CS6, O78 LPS and LTB in applicable age-groups in Bangladesh
- 3. To assess vaccine induced plasma IgA antibody responses against LTB, O78 LPS, CFA/I, CS3, CS6 and CS5 and IgG antibody responses against LTB and O78 LPS
- 4. To evaluate vaccine induced ALS IgA responses against O78 LPS (if sample volumes allow)
- 5. To assess adjuvant effect of dmLT on vaccine immune responses compared to responses when giving vaccine alone in descending age-groups in Bangladesh.

The secondary hypothesis of immunogenicity will be fulfilled if at least 50% or more of fully immunized young children and infants show significantly higher mucosal immune responses to at least two out of the five vaccine antigens tested (LTB, CFA/I, CS3, CS5, and CS6) by ALS IgA and or fecal SIgA/total SIgA assays compared to placebos.

A detailed statistical analysis plan for preparation of the final study report will be created and made final prior to database lock and unblinding for each age group.

Medical history and AEs will be coded using MedDRA® dictionary Version 16.1 or higher. The frequencies and percentages of participants with AEs will be summarized according to the coded terms of system, organ, class (SOC) and preferred term. Participant-wise data listings will be provided.

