### **Secondary Hypotheses:**

Immunogenicity

- 1. The vaccine regimens under testing will elicit mucosal immune responses to at least two of the antigens in 50% or more participants in at least one of the dosing regimens in young children or infants
- 2. The responses induced by the vaccine regimens tested will be higher and/or more frequent than the responses in the placebo group.
- 3. In the event that dmLT is used, adjuvanted vaccine will induce stronger (increased magnitude and/or breadth of response) intestinal and/or intestine-derived and/or plasma anti-LTB and anti-CF/CS antibody responses than the ETVAX alone in young children and infants.

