#### Immunogenicity Analysis

For all immunological analyses, the response rate and magnitude of antigen-specific responses will be analyzed after each immunization as specimen availability allows; as well as the cumulative response rate after two immunizations (i.e. response after either immunization). Response rates to the five primary antigens in the ETVAX vaccine (LTB, CFA/I, CS3, CS5, and CS6) will be further evaluated to address co-secondary immunogenicity hypothesis by analyzing the response rates to at least two of the five different antigens by ALS IgA and fecal SIgA and to at least one of the five different antigens by plasma IgA. In addition, other analyses summarizing response rates to multiple antigens may also be performed. These multiple antigen response rate analyses will be based on the results from antigen-specific responses, including different age cohorts. For example, only antigens with statistically significant and/or clinically meaningful vaccine induced responses may be included in the analysis of multiple common antigen analyses.

For descriptive analysis of the magnitude of responses, levels of antibodies against CFA/I, CS3, CS5, CS6 and LTB in ALS and fecal extracts as well as plasma will be determined for each individual during screening and in all post vaccination samples. The geometric mean (GM) of antibody levels and the GM of fold-rises (post vaccination / pre-vaccination) will be determined for each study group and comparisons made between pre- and post-vaccination levels. The response rate for ALS IgA, fecal SIgA, serum IgA and serum IgG will be determined as the proportion of participants having a  $\geq$ 2-fold increase in antigen-specific antibody levels between pre- and post-vaccination samples. Additionally, other fold increases (e.g. 3-fold and 4-fold) will be explored. If insufficient amounts of pre-immune ALS specimens are obtained from young children and infants, to allow direct comparison between pre- and post immunization specimens, antibody levels in post vaccination specimens will be compared with the geometric mean ALS antibody level against corresponding antigen in the same age group.

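### The fulfilment rule for the first secondary immunogenicity hypothesis is stated in two conflicting ways, and the choice between them can decide the result

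*Protocol*

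**What the plan says.** The hypothesis appears twice in the same form, under Hypothesis (if any) in the summary and under Secondary Hypotheses in the research description. Under that wording the vaccine should "elicit mucosal immune responses to at least two of the antigens in 50% or more participants in at least one of the dosing regimens"; either of the two youngest age groups is enough. It names no test, confidence bound or placebo comparison. The second hypothesis in the same lists says separately that vaccine responses will exceed placebo responses, without a threshold.

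The Data Analysis section (Overview and general design) restates the criterion. The hypothesis "will be fulfilled if at least 50% or more of fully immunized young children and infants show significantly higher mucosal immune responses"; these must cover two or more of five named antigens, measured "by ALS IgA and or fecal SIgA/total SIgA assays compared to placebos".

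The Immunogenicity Analysis section says how response rates will be evaluated to address the hypothesis: at least two of five antigens "by ALS IgA and fecal SIgA and to at least one of the five different antigens by plasma IgA". It gives no threshold. It adds that further multi-antigen summaries may be made, and gives as an example that "only antigens with statistically significant and/or clinically meaningful vaccine induced responses may be included". The same section defines a response as a two-fold or greater rise. It plans Clopper-Pearson intervals and comparisons with placebo, calls all immunogenicity comparisons exploratory, and applies Holm's correction across treatment groups in infants.

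**The concern.** The two fulfilment statements differ in three ways.

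- **Unit.** One asks whether any single regimen reaches 50%. The other has no regimen wording and appears to ask about all fully immunized children.
- **Age groups.** One is satisfied by young children or by infants. The other names both.
- **Placebo.** One has no comparator. The other asks that participants show significantly higher responses than placebo. Significance against a control group belongs to a group comparison, so no individual can be counted as showing it, and the proportion cannot be computed as written.

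The Immunogenicity Analysis section adds a difference in assays: it brings in plasma IgA, although the hypothesis is about mucosal responses, and joins ALS and fecal with and where the Data Analysis section has and/or.

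This is the only numerical criterion attached to an immunogenicity hypothesis. The protocol describes the trial as essential before deciding whether efficacy can be tested in children. If the wording stays open, the trial could be reported as meeting or missing its criterion on the same data, depending on which sentence is cited.

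**Working it through.** The protocol gives no error rate or power for the 50% criterion, so there is no stated figure to reproduce. The check asks how often each version would be met.

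**Inputs**
- Part C: four regimens (C1 to C4), 15 vaccinees each, 60 in total.
- Part D: five regimens (D1 to D5), 30 vaccinees each, 150 in total.
- If dmLT is not tolerated in toddlers, C3, C4, D4 and D5 are dropped (Part B text). C1, C2 and D1 to D3 remain.
- Assumption: one common true response rate p in every regimen, with regimens independent. The protocol gives no expected rate, so a range is shown.

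**Any-regimen version**

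A group of 15 reaches 50% with 8 or more responders, a group of 30 with 15 or more. Let a = P(X ≥ 8 | 15, p) and b = P(X ≥ 15 | 30, p). The chance that at least one of nine passes is 1 − (1 − a)^4 × (1 − b)^5. With five regimens it is 1 − (1 − a)^2 × (1 − b)^3.

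At p = 0.40, a = 0.2131 and b = 0.1754:
- Nine regimens: 1 − 0.7869^4 × 0.8246^5 = 0.854
- Five regimens: 1 − 0.7869^2 × 0.8246^3 = 0.653

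| True rate in every regimen | At least one of nine | At least one of five (no dmLT) |
|---|---|---|
| 30% | 25% | 14% |
| 35% | 56% | 36% |
| 40% | 85% | 65% |
| 45% | 98% | 89% |

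With about 10% loss (13 to 14 and 26 to 28 evaluable), the nine-regimen figure at 40% is 84% to 92%.

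**Data Analysis version**

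The significance clause cannot be computed per participant, so only the 50% part is evaluated, on two readings at p = 0.40.
- Pooled over 60 + 150 = 210 vaccinees: P(X ≥ 105 | 210, 0.40) = 0.0021, about 0.2%.
- Each age group must reach 50%: P(X ≥ 30 | 60, 0.40) × P(X ≥ 75 | 150, 0.40) = 0.0746 × 0.0083 = 0.0006, about 0.06%.

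**The same data under both.** Suppose one infant regimen shows 15/30 and the other 180 vaccinees respond at 15%. The first version is met. Pooled, the rate is (15 + 27)/210 = 20%, and the second is not.

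**Background check.** In Table 4 (Swedish adults, n = 20 placebo), 10% responded to two antigens, 5% to three and none to more, which gives 15% for two or more. At p = 0.15, a = 0.00061 and b = 0.00001, so the nine-regimen chance is about 0.25%.

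**Precision.** The 95% Clopper-Pearson interval is 27% to 79% for 8/15 and 31% to 69% for 15/30. Reaching 50% in one group says little about whether its true rate is 50%.

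**The case against.** Several points on the other side stand.

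- **No third rule.** A reader might infer that the Immunogenicity Analysis section is a third success rule. It is not: it has no threshold and nothing to pass, and its mention of ALS and fecal assays can be read as a list of assays. It only needs aligning.
- **Background alone does not satisfy the rule.** A reader might infer that background responses would meet the any-regimen version. At the only background figure in the protocol, that happens about 0.25% of the time. Background in Bangladeshi children may differ, but the protocol gives no figure for it.
- **Antigen selection does not touch the criterion.** The example of keeping only significant antigens concerns optional further analyses. The criterion itself names five fixed antigens.
- **Placebo comparison is not absent from the plan.** The second hypothesis and the Immunogenicity Analysis section provide for it, with intervals and Holm in infants. These do not, however, form part of the first hypothesis as stated in the hypothesis lists.
- **The setting is exploratory.** Safety is primary, progression between cohorts and age groups rests on safety review, and a detailed analysis plan is promised before unblinding. This lowers the stakes. It does not settle which of two contradictory protocol sentences the analysis plan should implement.
- **The 85% is conditional.** It assumes nine regimens with one common rate of 40%. Doses differ and the dmLT cohorts may be dropped, hence the range above.

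**Conclusion.** The contradiction holds on the text alone: two fulfilment rules for one hypothesis, differing in unit, age groups and comparator, one of them not computable as written. Its effect can be decisive. Under an assumed common, independent true rate of 40%, the any-regimen version is met about 85% of the time (65% with the five non-dmLT regimens), against about 0.2% for the other read as pooled vaccinees. At 30% and 35% the nine-regimen figures are 25% and 56%.

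The weakness of the any-regimen version is selecting the best of several small groups on a point estimate. It is not a false positive driven by background. Because the comparisons are declared exploratory and safety is primary, this is a should-fix.

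**What to change.** State one rule in both hypothesis lists and in the Data Analysis overview, and align the Immunogenicity Analysis section with it.

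1. **Participant level:** a responder has a two-fold or greater rise to at least two of the five fixed antigens (LTB, CFA/I, CS3, CS5, CS6) by ALS IgA and/or fecal SIgA.
2. **Regimen level:** report the responder rate for each regimen, separately for Parts C and D, with the planned Clopper-Pearson interval and Fisher comparison with placebo. Apply Holm across regimens in infants, as already planned.
3. **Claim:** state that 50% or more in the best of several regimens is an observed benchmark, and is not evidence that the true rate is 50% or more unless the interval supports it.
4. **Other analyses:** keep plasma IgA and any analysis on selected antigens supportive or exploratory.

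Making a lower 95% limit above 50% the pass rule is not recommended. It would need 12/15 or 21/30, and a regimen with a true rate of 60% would then pass only 9% or 18% of the time, in a trial not sized for that test.

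The cost is wording in the protocol and analysis plan, settled before unblinding. The claim becomes slightly harder to make. No new data are needed.
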